## 6.2 Information bias

Information bias is a distortion in the estimate of association between risk-factor and disease that is due to systematic measurement error or misclassification of patients on one or more variables, either risk-factor or disease status. This could occur in this study if HCPs do not report certain types of events of potential interest because they feel they are not related to the safety of the medication. As a result, we will check key data of the CRF against the source data for a defined percentage of patients to determine how well the information provided in the Eurartesim™ Registry matches their medical records.

Misclassification of timing of exposure; it may be difficult to ascertain at exactly which point throughout the pregnancy the exposure to Eurartesim™ occurred.

Outcome misclassification; there is a likelihood that pregnancy losses occurring early in gestation (i.e. the first trimester) may not be recognized and/or reported. Additionally, the reporting HCP may not always know the health status of aborted fetuses.

Ascertainment of elective abortions; legislation in some countries may prohibit the collection of identifiable data. Elective abortion is currently legally available in all European countries, except Malta. All of these countries allow abortion to save the life of a mother and most for other reasons, including on-demand up to 18 weeks of gestation (BBC News, 2007). As a result, it seems unlikely that assessment of elective abortion (without additional information for the reasons associated with abortion) would violate local laws in the countries being targeted for patient enrolment. In addition, however, prior to initiation of recruitment in a given country, the Sponsor and it's designated CRO partner, REGISTRAT-MAPI, will review local laws for each country and discuss the specific questions to be used on this topic with the local investigators and relevant ethical committees and authorities to ensure that the necessary wordings are considered with regards to current interpretation of ethical standards and applicable local laws.

Information bias could also occur in this registry regarding the collection of lifestyle data, such as BMI, radiation exposure, smoking status, alcohol consumption and recreational drug use. Patients may under-report these factors, which is an inherent limitation associated with the collection of lifestyle data.

## 6.3 Confounding bias

Concomitant infections/diseases and medication use may have a potential confounding influence upon the pregnancy outcome and maternal complications. In order to control for potential confounders, details of any concomitant infections/diseases and medication use will be collected and pregnancy outcomes will be analysed according to these parameters.

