
## 5.4 Sample Size Calculation

Data for this pregnancy Registry will be regularly collected until the sample size required to detect a 2-fold or greater increase relative to the expected background rate of all birth defects and spontaneous abortions is reached. This will provide an adequate sample to ensure understanding of maternal drug safety. The Registry will be closed to new entries once this number of women with validated follow-up information has been reached and in agreement with the EMA; the data will be transferred to another independent Registry, if in acceptance with the other Registry, and according to ethical standards and national legislation at that point in time. These data will then be compared to background rates to see if there has been a significant increase in birth defects or pregnancy loss amongst these patients. A sensitivity analysis will be performed on the data to check other contributing factors.

The following sample size is derived to detect a clinically significant difference (i.e. a >2x increase in the outcome of concern) relative to expected background rates. In Europe, the assumed background risk of all reported birth defects is 23.719 per 1,000 births (EUROCAT, 2009) and the background rate of spontaneous abortion is 85.6 per 1,000 (Tata *et al*, 2005). Thus, assuming 80% power, 0.05 significance level (one-sided) and a loss to follow-up rate of 5%, we would require 376 pregnant women exposed to EurartesimTM in order to be able to detect a 2-fold or greater increase in birth defects and a 1.5-fold or greater incidence in spontaneous abortions with a one-group test. Calculations are based on a normal approximation to a Binomial distribution (equivalent to a chi-square test). Employing a 5% loss to follow-up rate is deemed appropriate as

utilising the services of ProClinica (refer to Section 7.3) to actively follow-up patients via direct patient contact should reduce the degree of loss to follow-up in this Registry.

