#### 4-weeks post-enrolment and 4-weeks prior to expected due date:

- Date of the visit.
- Serious adverse events (drug related or not) in the mother since previous visit/contact.
- Exacerbation of pre-existent clinical condition in the mother since previous visit/contact.
- Comorbidities in the mother since previous visit/contact.
- Concomitant medication use in the mother since previous visit/contact.
- Maternal complications since previous visit/contact.
- Fetal complications since previous visit/contact; any spontaneous abortions (≤28 weeks gestation), elective abortions, ectopic pregnancies, late fetal or neonatal deaths (>20 weeks gestation), premature deliveries (≤37 completed weeks).

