#### At end of pregnancy:

- Date of the end of pregnancy.
- Maternal complications since previous visit/contact.
- Maternal mortality.
- Stillbirth (>28 weeks gestation).
- Early neonatal mortality.
- Gestational age at delivery (estimated from the last menstrual period).
- Live births.

- Infant birth weight (adjusted for gestational age).
- Infant major and minor birth defects (primary outcome of interest).
- Serious adverse events (drug related or not) in the mother or the infant since previous visit/contact.
- Exacerbation of pre-existent clinical condition in the mother since previous visit/contact.
- Comorbidities in the mother since previous visit/contact.
- Concomitant medication use in the mother since previous visit/contact.

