#### Primary analysis

In accordance with the primary objectives of the study and the way the study was powered, the main focus of the statistical analysis will be estimation of the incidences of birth defects and spontaneous abortion. 95% confidence intervals will be computed around these incidences in order to judge whether there is an increase of these incidences as compared to background risks.

In order to control for potential confounders, birth defects and spontaneous abortion will be described according to parameters such as concomitant infections/diseases and medication use. For spontaneous abortions, women who discontinued the study prior to delivery will not be taken into account in the primary analysis. A sensitivity analysis will be performed considering all patients, assuming that women who discontinued the study prior to delivery had experienced spontaneous abortion; this will provide us with the highest estimation of incidence of spontaneous abortion (i.e. the worst-case scenario).

In the same way, in the primary analysis, incidences of birth defects will be analysed without considering patients who discontinued the study prior to 14 weeks after the end of pregnancy. A sensitivity analysis will be performed on all patients assuming that women who discontinued the study prior to 14 weeks after the end of pregnancy had experienced birth defects.

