#### Analytical methods

Continuous variables will be described by their mean, standard deviation, median, quartiles 1 and 3, extreme values (minimum and maximum) and the number of missing data.

Categorical variables will be described by the total and percentage of each response method and the number of missing data.

Continuous variables will be compared using Student's t-test (2 groups) or variance analysis (>2 groups). If the conditions for applying these tests are not met (normality, homoscedasticity), the Mann-Whitney, Wilcoxon (2 groups) or Kruskal-Wallis (>2 groups) non-parametric tests will be used.

Categorical variables will be compared between subgroups using the Chi-2 test if the theoretical total of each class studied is greater than 5. Otherwise Fisher's exact test will be used.

The ordinal variables will be compared between subgroups using a Cochran-Mantel-Haenszel test.

Hypothesis formulation will be bilateral. The tests will be performed for a first species alpha risk of 5%.

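### Sections 5.7 and 6.3 control confounding with disease and medication data that are mostly recorded after exposure and over a period that the outcome itself cuts short

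*Protocol*

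**What the plan says.** Protocol section 6.3 names concomitant disease and medication as potential confounders of pregnancy outcome and maternal complications. Its remedy is that "details of any concomitant infections/diseases and medication use will be collected and pregnancy outcomes will be analysed according to these parameters". Section 5.7 (Primary analysis) gives the same purpose for the two main outcomes: "birth defects and spontaneous abortion will be described according to parameters such as concomitant infections/diseases and medication use". Section 5.7 (Pregnancy-related information) extends this to pregnancy outcomes in general and adds lifestyle factors. Under Analytical methods, "Categorical variables will be compared between subgroups using the Chi-2 test", with Fisher's exact test for small expected counts, two-sided at 5%.

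The data behind these strata are set out in section 5.5 and Table 1:

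- **Enrolment:** medication in the 30 days before conception, other treatment for malaria, significant medical history, and previous or concurrent maternal complications.
- **Visits 2 and 3:** "Comorbidities in the mother since previous visit/contact", and medication over the same interval.
- **Visit 4, end of pregnancy:** "Concomitant medication use in the mother since previous visit/contact", and comorbidities likewise.
- **After Visit 4:** neither item is collected.

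Section 7.4.1 counts a spontaneous abortion as a loss up to 28 weeks.

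**The concern.** A confounder of the effect of Eurartesim has to be in place before, or at, exposure. Apart from the enrolment items, the disease and medication data start at enrolment, which comes after exposure for women treated in pregnancy. They stop when the pregnancy stops, so the outcome fixes how long a woman can be observed to start a drug or fall ill. A woman who miscarries soon after enrolment has a few weeks; a woman who delivers at term has about 30. Section 5.5 also allows enrolment when the outcome is already known, and a woman enrolled after a loss has no such time at all.

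This is the usual immortal-time problem. Items noted at Visit 4 may also result from the loss or from preterm labour. Spontaneous abortion is one of the two outcomes on which section 5.4 sizes the registry, and the registry has no comparison group. If these strata are read as control of confounding, an artefact could be taken for a protective co-medication, or for evidence that confounding has been ruled out.

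**Working it through.** **The plan's own figures.** Section 5.4 gives a "background rate of spontaneous abortion is 85.6 per 1,000" and a "background risk of all reported birth defects is 23.719 per 1,000 births", and works on "assuming 80% power, 0.05 significance level (one-sided) and a loss to follow-up rate of 5" per cent. The total of 376 is recovered by an exact one-sided binomial test for a doubling of birth defects: the smallest n with 80% power is 357, and 357/0.95 = 375.8, rounded up to 376. (The normal approximation named in 5.4 gives 328, or 346 after loss; that does not bear on this point.) I use 357 evaluable women and q = 0.0856. The protocol states no figure for the bias itself.

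**Assumptions, none of them from the protocol.** Enrolment is uniform over weeks 6 to 12, losses are uniform 1 to 12 weeks after enrolment, and other births occur at week 39. The drug has no effect on outcome. It is started at a constant rate h of 0.5 to 5% per week, and a fraction b of women are already users at baseline (0, 20 or 40%). A user is anyone with recorded use up to the end of pregnancy.

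**Formulas.**

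- Chance of starting before a loss: e_L = 1 − [exp(−h) − exp(−12h)]/(11h)
- Chance of starting before a birth (27 to 33 weeks of follow-up): e_B = 1 − [exp(−27h) − exp(−33h)]/(6h)
- Classed as user: L = b + (1 − b)e_L after a loss, B = b + (1 − b)e_B after a birth
- Risk in users: qL/[qL + (1 − q)B]
- Risk in non-users: q(1 − L)/[q(1 − L) + (1 − q)(1 − B)]

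**Worked case, h = 1% per week, b = 0.**

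- e_L = 1 − (0.9900 − 0.8869)/0.11 = 0.0625
- e_B = 1 − (0.7634 − 0.7189)/0.06 = 0.259
- Users: 0.00535/(0.00535 + 0.2369) = 2.2%
- Non-users: 0.0803/(0.0803 + 0.6775) = 10.6%
- Risk ratio 0.21; the truth is 1.0

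With b = 20%, L = 0.250 and B = 0.407. The risks are 5.4% and 10.6%, and the risk ratio is 0.51.

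**Full range.** Each cell gives the risk ratio and, after it, the share of simulated registries of 357 women in which an uncorrected chi-square test is falsely significant at 5%.

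| Starts per week | b = 0 | b = 20% | b = 40% |
|---|---|---|---|
| 0.5% | 0.22; 36% | 0.67; 14% | 0.79; 10% |
| 1% | 0.21; 78% | 0.51; 40% | 0.65; 24% |
| 2% | 0.19; 98% | 0.36; 81% | 0.47; 59% |
| 3% | 0.17; >99% | 0.28; 95% | 0.37; 82% |
| 5% | 0.13; >99% | 0.19; 99% | 0.24; 96% |

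**Other timings.** With enrolment at week 8 or 12, losses spread from week 6 to week 14, 20 or 28, delivery at 40 weeks and 20 to 80% use over a full pregnancy, the risk ratio is 0.02 to 0.31 with no baseline users and 0.09 to 0.63 with 20%.

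**Is the coding the cause?** In a simulation of 2,000,000 pregnancies with enrolment at weeks 6 to 24, ever/never coding gives 0.20, 0.17 and 0.12 for 20, 50 and 80% use. Counting use only from its start, within gestational week, gives 0.99, 1.01 and 1.01 in the same data.

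**The case against.** The strongest reply is that the protocol never says ever/never. It fixes no window and announces a statistical analysis plan. That plan could use only the pre-conception record, a common early window, or time-updated use, and the bias would then not arise. A reader might infer that the protocol commits the registry to the biased coding; the text does not support that. What remains is that 6.3 makes all the collected disease and medication data the confounder parameters, and most of those data follow exposure whatever the coding.

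Other replies also have force:

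- **Baseline data exist.** The pre-conception medication window is the same length for every woman. Baseline use dilutes the bias, so 0.13 to 0.22 is one corner of the range. It does not remove the bias in any case tried.
- **Testing is not certain.** For spontaneous abortion, Primary analysis says described, and Analytical methods names no outcome. At 0.5% starts per week Fisher's test would usually replace chi-square, which lowers false significance only from about 37% to 33%.
- **Direction.** A reader might infer a protective artefact for every drug. Treatment given because of a threatened or actual loss pushes the other way, so that is not supported.
- **Start dates.** Section 5.5 lists none for medication or comorbidity, but section 7.4 says the CRF is still to be developed, so their absence cannot be asserted.

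**Conclusion.** The point holds in a limited form. Followed as written, sections 5.7 and 6.3 use mostly post-exposure items, whose recording time depends on the outcome, as control of confounding. For spontaneous abortion, and less so for premature delivery, strata coded ever/never would show an association where none exists. Under the assumed timings the risk ratio is about 0.13 to 0.22 without baseline users and about 0.2 to 0.79 with 20 to 40%, with false significance in about 10% to over 99% of registries if tested. These sizes rest on assumed enrolment weeks, loss timing, start rates and baseline use, and on ever/never coding.

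A reader might go on to infer that the registry's main result is biased. It is not: incidence with its 95% confidence interval against background does not use these strata, and defects in live births are little affected. The damage is confined to the comparisons by disease and medication, which are the registry's stated answer to confounding. That is enough to justify changing the wording.

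**What to change.** In sections 5.7 and 6.3, form confounder strata only from conditions and medication present before or at first Eurartesim exposure: pre-conception medication, medical history, and any condition or drug with a start date on or before exposure. In section 5.5 and the CRF, record a start date for each concomitant medication and comorbidity. Because the enrolment medication question covers only the 30 days before conception, it should also reach forward to the date of first exposure.

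Report later-starting items descriptively and do not call that control of confounding. Alternatively, treat them as time-dependent from their start up to the outcome, leaving out any that began on or after its onset.

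The cost is one date field, a slightly longer enrolment question and a few sentences. The downside is fewer women in the user strata, and so less precise comparisons.

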## 6.4 Lost to follow-up

Outcomes among pregnancies lost to follow-up could differ from those with reported outcomes. Patients will be considered lost to follow-up if a patient's expected delivery date has passed and outcome data have not been entered into the Registry within one year following the expected delivery date. Reasons of loss to follow-up will be documented. In order to investigate this further and determine the extent to which the results may be affected by loss to follow-up, a sensitivity analysis will be executed, in the same manner as described in the 'Primary analysis' part of Section 5.7.

In order to reduce the number of lost to follow-up patients, the option for each patient to be contacted by a specialized patient management unit (ProClinica, refer to Section 7.3) run by our CRO partner has been built into the Registry. Such contact will provide ongoing patient contact to remind the patient-participant of the importance of her ongoing participation in the Registry.

## 7. Study Conduct

## 7.1 Site initiation

A study kit will be given to each HCP who confirms his/her participation and completes the necessary administrative procedures.

The study kit contains the following:

- Protocol
- Patient information sheet and consent form
- (Serious) Adverse Event Report
- Contact Order Form (COF)
- HCP enrolment form
- Pre-paid envelopes

On reception of the study kit, a HCP initiation phone call will be performed by the responsible ERA to review the study and its logistic and administrative aspects.

As they are completed, the HCP enrolment forms will be returned to RM-EU by the HCPs in prepaid envelopes just after the visit.

## 7.2 Patients' inclusion

The HCP will include all patients meeting the inclusion criteria and agreeing to take part in the Registry. During this recruitment phase, and for each patient, the HCP will:

- Explain the Registry to the patient (in particular the objective of the registry and its observational nature), give her a patient information sheet, a Consent Form and a Contact Order Form and ask the patient to read, fill in and sign them to confirm her agreement.
- Fill in the enrolment CRF of the registry.
- Send by fax or mail the completed Contact Order Form to the unit in charge of the patient follow-up.

These agreements must be obtained for the recruitment and follow-up of both the patient and her infant.

For non-included patients meeting the selection criteria, the HCP will collect few data (e.g. age, ethnicity, gestational time of Eurartesim™ exposure) in a short form (patient

log) of the Registry to collect the reason of non-inclusion and in order to determine if the study population correspond with the wider population.

## 7.3 Follow-up

During follow-up visits/contacts, the HCP will:

- Fill in the follow-up CRF of the registry.

Women will visit their antenatal clinic for assessment of safety parameters at enrolment, 4 weeks post-enrolment, 4 weeks pre-delivery, at delivery and at 6 weeks post-delivery. Infants will be followed up at 6 weeks, 14 weeks and 12 months after birth. Infant neuro-developmental assessment will be performed at 14 weeks and 12 months after birth. Safety assessments will include monitoring and recording all AEs and SAEs up to 12 months after delivery; in the case of the reporting of an adverse outcome, additional information regarding relevant medical history and family history will be collected.

## Ethical and Personal Data Protection considerations regarding contacts with Patient:

Patients or their legal representative are asked to complete and sign a "Contact Order Form". This "Contact Order Form" is sent to ProClinica. From an ethical and personal data protection perspective, this written patient agreement provides evidence that the participant and/or his legal representative voluntarily communicated his personal and his HCP's contact details to the ProClinica unit. This will allow them to perform the contacts as described in the protocol during the study follow-up period.

Additionally, by this form patients are informed about their rights, as required by the Data protection regulations. Given that the patient has the right to refuse to answer the questionnaire or individual questions at any time and may ask the ProClinica unit to end all future contacts, it can be considered that consent to be contacted and to provide health information is tacitly renewed with each assessment.

The ProClinica unit never transfers patients' nominative data to the study sponsor, the monitor or any other third party not directly involved in its mission. Patients' health data are collected in a de-identified way, using a study identification code (e.g. patient number, site number). The patients' contact details are never linked to the patients' health data and the patients' contact details, including Contact Order Forms, are erased at the end of the study from all data support systems (computer and paper).

Page **38** of **56** 

All interviewers working on the study have signed a professional secrecy agreement, are trained specifically to the study and to data privacy rules, as well as supervised and quality controlled throughout the study. The Medical Direction of ProClinica unit will intervene when necessary. Patient return calls by a HCP can be performed when needed.

The ProClinica unit personal should not be considered as a substitute for the investigator or the treating HCP in their patient follow-up responsibilities. Interviewers never interfere with the usual relationship between patients and healthcare professionals. On the contrary, they promote it. They are required to not comment any prescription or giving any advice or response to medical/study questions (except for those expressly included in their mission for the project). If a medical question or problem arises during a telephone call, the patient (or the legal representatives) is advised to contact his/her HCP.

REGISTRAT-MAPI has declared its ProClinica unit activities of direct contact with patients in studies and patient management programs to the French Data Protection Authority (CNIL) (refer to Appendix 2). This declaration (statement number 794019) covers the management of patient contact details throughout the European Union (i.e. administrative data). Collection of health data should be submitted to competent authorities according to each country specific regulations.

The processing of personal data is performed in accordance with REGISTRAT-MAPI commitment (statement number 1432965) to comply with the French standards for Pharmacovigilance activities (*Autorisation unique AU-013 pour le traitement des données à caractère personnel dans le cadre de la pharmacovigilance*).

